- The de-identified, but self-described, chronic ailments will be used with the scan results to broadly identify cohorts that may benefit from screening for asymptomatic disease.
- What operating cost burden is required to sustain a mobile screening project and what is the minimum utilization required to justify it?
- The operating costs of the study will be captured in order to inform an analysis of the financial constraints for deployment of mobile screening systems into local underserved communities.
- What portion of the asymptomatic patients with advanced disease will be willing to learn about clinical trials?
- Analysis of the posttest behavior of participants by their enrolling to learn more about clinical trials will measure the efficacy of using this method to educate the at risk population about clinical trials and ultimately inform decisions about how trial participants may be recruited in the future.
- What portion of the patients take advantage of free online diet support?
- Lifestyle changes are challenging as it is difficult to engage patients in the weeks following any testing. Tracking of the number who take advantage of the follow-up support will help guide future efforts to develop educational materials.

Patient Selection Criteria

The screening will be available to adults who self-select and who meet the inclusion criteria. The project will stop at 3 months or 1,000 patients, whichever occurs first. The goal is to

examine whether a self-referral design can serve as a cost effective patient centered wellness screening model.

Who may participate

- Adults 18 and over
- Patients with no diagnosis of liver disease
- Patients with any of these self-identified chronic conditions
 - Type 2 diabetes
 - Metabolic syndrome
 - Cardiovascular disease
 - Pre Diabetes
 - Sleep apnea
 - Digestive disorders
 - Osteoporosis
 - Polycystic ovarian syndrome
 - Psoriasis

Who may not participate

- Age less than 18
- Pregnant women
- Anyone with an implanted electronic device such as a defibrillator
- Morbidly obese, BMI 40 or greater
- Anyone not personally able to give informed consent
 - Non English speakers, no translator is available

Trial Candidate Outreach

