The data from the study will be used to support future financial modeling and to provide baselines for programs to educate patients about clinical trials, diet, and lifestyle changes delivered electronically. Since there is no existing measure, an a-priori power analysis is not overly instructive, but based on an assumed normal distribution the study seeks to enroll no fewer than 400 participants to yield a minimum theoretical power of around 0.8 and may include up to a maximum of 1,000 patients.

The study will also produce data on the incidence and staging of NAFLD and NASH, as indicated by their FibroScan scores, and will track, in aggregate, their response to information about clinical trials and dietary support delivered through online resources. This data will not be informed by the patient record as no personally identifiable data will be collected.

The dataset will include demographic information and general ethnicity so aggregate subtotals of the various populations may be examined for additional insights to inform future investigations.

DATA COLLECTION:

Demographics:

After signing the consent form the research subjects will fill out a basic form to provide demographic information, including sex, age, and race/ethnicity. We will measure height and weight prior to CAP/FibroScan testing.

Metabolic Syndrome:

Subjects will use a form to check YES or NO for comorbid components of the metabolic syndrome that they may or may not have:

- Obesity/overweight
- Diabetes mellitus
- Hypertension
- Hypercholesterolemia
- Hypertriglyceridemia
- Gout or elevated uric acid

Other Health Conditions:

Subjects will use a form to check YES or NO for other health conditions they may or may not have:

- Heart disease
- Heart attack
- Arrhythmia
- Stroke
- Arthritis
- Osteopenia/osteoporosis
- Hypothyroidism
- Low Vitamin D
- Low testosterone
- Menopausal state
- Inflammatory bowel disease (ulcerative colitis or Crohn's disease)
- Cancer
 - Skin: melanoma
 - Skin: basal cell or squamous cell cancers
 - Other type of cancers: lymphoma; leukemia; head or neck; thyroid; brain; breast; lung; stomach; colon; liver; ovary; uterus; prostate; bone

Diet:

Subjects will fill out a form using a 5-point scale of the frequency of their average weekly dietary intake of specific food types: (A. 0 days, B. 1-2 days, C. 3-4 days, D. 5-6 days, E. 7 days per week)

- Proteins: eggs, cheese, beans, fish, chicken, turkey, beef, pork

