- Starchy carbohydrates: breads, rolls, pasta, cereals, potatoes, rice, corn, peas, lima beans
- Non-starchy vegetables: lettuces, kale, carrots, green beans, broccoli, peppers, onions, cucumber
- Fats: butter, margarine, avocado, oils (olive, safflower, cottonseed, peanut, sesame, walnut)
- Nuts: peanuts, walnuts, cashews, almonds, macadamias, peanuts
- Sugars or Syrups: sugar, high fructose corn syrup (sodas), maple or corn syrups
- Fast food meals
- Eating out at restaurants

Exercise:

Subjects will fill out a form using a 5-point scale of the frequency of their average weekly exercise:

(A. 0 days, B. 1-2 days, C. 3-4 days, D. 5-6 days, E. 7 days per week) ○ Cardiovascular: brisk walking, jogging, biking, treadmill, stationary bike, stair stepper, elliptical, swimming laps ○ Strength: weight lifting, resistance machines or cords

Alcohol:

Subjects will fill out a form quantifying their average weekly total of alcoholic drinks:

(1 drink= 12 oz. beer, 6 oz. wine, 1.5 oz. hard liquor; 3 oz. brandy, sherry, liqueur):

- None
- 1-2 drinks/week
- 3-4 drinks/week
- 5-6 drinks/week
- 7-8 drinks/week
- 9-10 drinks/week
- 10-12 drinks/week
- 13-14 drinks/week
- 14-20 drinks/week
- 21 or more drinks/week

Other Liver Diseases:

Subjects will check YES or NO for other liver-related diseases that they may or may not have:

- Hepatitis B alone
- Hepatitis B with Hepatitis D
- Hepatitis C
- Hepatitis E
- Autoimmune hepatitis
- Primary biliary cholangitis
- Primary sclerosing cholangitis
- Iron overload
- Alpha-1-antitrypsin deficiency

Reporting of CAP-FibroScan Results to Participating Subjects:

A trained individual will perform the CAP-FibroScan according to the FDA-approved, manufacturer's protocol. A licensed hepatologist will determine the degree of fibrosis and will review the results and the steatosis based on the values in the following tables:

Transient Elastography (TE):

Disease	F0-F1	F2	F3	F4
NAFLD/NASH	≤ 7.0	≤ 7.5	≤ 10.0	≤ 14.0

Reference: Current Gastroenterology Reports. 2014; 16: 372

TE Interpretation: The subject's liver stiffness score in kPa units shows:

- **F0:** No liver fibrosis
- **F1-2:** Mild-Moderate liver fibrosis
- **F3:** Severe liver fibrosis
- **F4:** Cirrhosis

Controlled Attenuation Parameter:

Steatosis Grade	% Steatosis on Liver Biopsy	CAP Value
Mild (S1)	5-33%	225-275 dB/M
Moderate (S2) to Severe (S3)	>33% >66%	275-400 dB/M

Reference: World J Gastroenterol. 2016; 22: 7236

CAP-FibroScan Experience and Satisfaction Survey:

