 - No fat but evidence of liver stiffness
 - Fat without liver stiffness
 - Fat with liver stiffness
 - Stiffness values indicative of cirrhosis
 - Stiffness values indicative of fibrosis without cirrhosis

NOTE: no individual follow up or track will be done as not personally identifiable information will be captured or retained.

2. The secondary goal is to determine factors that are statistically significantly associated with the presence or absence of fat with or without increased liver stiffness.

We will analyze data using a standard statistical software package, Stata® 12.1 (Stata Corp, College Station, TX). We will express continuous variables using the mean ± standard deviation, and we will test the null-hypothesis using the Student t-test. We will compare categorical variables using contingency table analysis. For all statistical tests, we will define a two-sided p-value of ≤0.05 as statistically significant. We will perform multivariate analysis of all risk factors found to be statically significant (p ≤0.05) using univariate analysis.

This exploratory goal seeks to determine the degree of satisfaction of subjects who undergo a screening CAP-FibroScan free of charge.

We will calculate the frequency of answers for each of the five items reflecting subjects' likelihood of:

- recommending this test to a friend or family member.
- sharing their results with their doctor.
- consulting with a liver specialist.
- seeking information about FDA-approved clinical trials of therapies for non-alcoholic fatty liver disease.
-

We will not perform statistical analyses for these descriptive data.

Disease Staging

The disease staging to be analyzed will be based upon these breakpoints from the FibroScan test. The test scores will be translated into these staging ranges for analysis.

Transient Elastography (TE):

Disease	F0-F1	F2	F3	F4
NAFLD/NASH	≤ 7.0	≤ 7.5	≤ 10.0	≤ 14.0

Reference: Current Gastroenterology Reports. 2014; 16: 372

TE Interpretation: The subject's liver stiffness score in kPa units shows:

- **F0:** No liver fibrosis
- **F1-2:** Mild-Moderate liver fibrosis
- **F3:** Severe liver fibrosis
- **F4:** Cirrhosis

Controlled Attenuation Parameter:

Steatosis Grade	% Steatosis on Liver Biopsy	CAP Value
Mild (S1)	5-33%	225-275 dB/M
Moderate (S2) to Severe (S3)	>33% >66%	275-400 dB/M

Reference: World J Gastroenterol. 2016; 22: 7236

DATA COLLECTION

Demographics:

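### The alcohol item has no recall period and no past-drinking answer, so the secondary alcohol association may be biased, in a direction that depends on unmeasured facts about former drinkers

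*Combined protocol and SAP*

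**What the plan says.** The Alcohol item appears in the protocol's data collection section and again in the SAP's DATA COLLECTION section, in the same words: "Subjects will fill out a form quantifying their average weekly total of alcoholic drinks". There are ten answers. The first is *None*, the next is "1-2 drinks/week", and the last is 21 or more. Neither version gives a period over which to average, and neither document asks about past or lifetime drinking anywhere else.

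The analysis that could use this item is item 2 under Data Analysis in the SAP, which aims to "determine factors that are statistically significantly associated with the presence or absence of fat with or without increased liver stiffness". Alcohol is not named there. The SAP gives neither a coding for the alcohol answers nor a reference group. On testing it says "we will define a two-sided p-value of ≤0.05 as statistically significant", and then "We will perform multivariate analysis of all risk factors found to be statically significant" on univariate analysis.

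Two other provisions matter. Eligibility (Who may participate) requires "Patients with no diagnosis of liver disease" together with at least one self-identified chronic condition. The protocol (Intended Use of the Data) and the note under Data Analysis item 1 in the SAP rule out both use of the patient record and individual follow-up.

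**The concern.** Someone who used to drink and now answers about present habits has only *None* to tick, the same box as someone who never drank. The missing recall period adds a second uncertainty. Another former drinker might average over a longer span and tick a higher band, so people with the same history may be classified differently.

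If the two groups within *None* differ in liver stiffness or fat, every comparison of drinkers with *None* is distorted. The plan's selection rule can make this worse: a weakened alcohol association may miss the univariate p-value cut-off and drop out of the multivariate analysis, leaving the other associations unadjusted for alcohol. Drinking history not asked at intake cannot be recovered, because there is no follow-up and no link to records.

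**Working it through.** **The plan's own figure.** The protocol states that "the study seeks to enroll no fewer than 400 participants to yield a minimum theoretical power of around 0.8". No effect size, standard deviation or rate accompanies it, so it can be neither reproduced nor refuted. Worked backwards for two groups of 200 at two-sided 0.05, it corresponds to a standardized difference of (1.960 + 0.842) × √(2/200) = 0.28. It says nothing specific about alcohol.

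**Formula for the bias.** Let f be the share of former drinkers within *None*. Then

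- rate in *None* = (1 − f) × p_never + f × p_former
- true minus observed risk difference = f × (p_former − p_never)

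The sign depends entirely on p_former − p_never. The documents give neither f nor any of the rates, so what follows rests on assumptions.

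**Size, for increased stiffness.** Assumed rates: never 8%, light current drinkers 10% (true ratio 0.10/0.08 = 1.25), heavy current drinkers 16% (true ratio 0.16/0.08 = 2.0). Each cell shows the light ratio / heavy ratio, that is 0.10 and 0.16 divided by the rate in *None*.

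| Former-drinker rate | f = 10% | f = 25% | f = 40% |
|---|---|---|---|
| 6% | 1.28 / 2.05 | 1.33 / 2.13 | 1.39 / 2.22 |
| 8% | 1.25 / 2.00 | 1.25 / 2.00 | 1.25 / 2.00 |
| 10% | 1.22 / 1.95 | 1.18 / 1.88 | 1.14 / 1.82 |
| 12% | 1.19 / 1.90 | 1.11 / 1.78 | 1.04 / 1.67 |
| 16% | 1.14 / 1.82 | 1.00 / 1.60 | 0.89 / 1.43 |
| 20% | 1.09 / 1.74 | 0.91 / 1.45 | 0.78 / 1.25 |

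Example: former rate 12% and f = 25% give a rate in *None* of 0.75 × 0.08 + 0.25 × 0.12 = 0.09, so the ratios are 0.10/0.09 = 1.11 and 0.16/0.09 = 1.78.

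**When the sign reverses.** Apparent protection needs f > (p_current − p_never)/(p_former − p_never). For light drinkers the threshold is 0.02/0.02 = 100% at a former rate of 10% (so it cannot happen), 0.02/0.04 = 50% at 12%, 0.02/0.08 = 25% at 16%, and 0.02/0.12 = 17% at 20%. For heavy drinkers it is 0.08/0.12 = 67% even at 20%.

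**Effect on the univariate screen.** This is a separate illustration with a larger assumed effect: 30% of never-drinkers and 45% of current drinkers have the outcome (odds ratio 1.91), with 160 of 400 participants in *None* and 240 current drinkers. With no former drinkers in *None*, the power to pass p ≤ 0.05 is 0.86. Each cell shows the observed odds ratio and power.

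| Former-drinker rate | f = 10% | f = 20% | f = 40% |
|---|---|---|---|
| 25% | 1.96, 0.88 | 2.00, 0.90 | 2.10, 0.94 |
| 30% | 1.91, 0.86 | 1.91, 0.86 | 1.91, 0.86 |
| 45% | 1.78, 0.78 | 1.66, 0.67 | 1.45, 0.43 |
| 55% | 1.70, 0.71 | 1.52, 0.51 | 1.23, 0.17 |

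If former drinkers are taken out of *None*, the odds ratio returns to 1.91 on a smaller reference group. With 144, 128 or 96 never-drinkers (160 less 10%, 20% or 40%) against 240 current drinkers, the same two-proportion calculation gives power of 0.84, 0.81 or 0.72.

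**The case against.** A reader might infer that the alcohol association *is* biased toward no effect or apparent protection. The documents do not support that. They give neither the share of former drinkers nor their rates, and the second set of tabulated rows (former equal to never) shows no bias at all. The 16–20% rows give every former drinker, including those who drank lightly, a risk at or above that of heavy current drinkers. At 10–12% nothing reverses for shares up to 40%, and heavy drinking stays harmful in every cell.

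Other points that stand:

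- That the item asks about current drinking is an inference, since no period is stated. So is the use of *None* as the reference. The SAP plans contingency tables, which need no reference category, although *None* remains a mixed group under any coding.
- Excluding diagnosed liver disease removes former drinkers with known liver damage, who would probably contribute most to an excess. It reduces the problem without removing it, because those with undiagnosed disease remain eligible.
- The contrast that can reverse is barely testable anyway. For 8% versus 10%, power is about 0.10 with 160 and 240 participants, and about 0.18 with 400 and 600, even with perfect classification.
- The ratios above are for stiffness. Nothing equivalent has been worked out for fat, which may behave differently after someone stops drinking.

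A reader might also infer that the main estimates of nonalcoholic disease are compromised by this item. The primary proportions do not use it. No alcohol threshold is applied to them, so current heavy drinkers are counted as well. That is a different question, which a never/former split would not settle.

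**Conclusion.** The defect is real and limited in scope. As the form stands, never- and former drinkers can share one answer, the averaging period is undefined, and the SAP has no means of separating the groups later. The possible bias is confined to the secondary association analysis, where alcohol is an implied rather than a named factor.

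Its direction is conditional on how former drinkers compare with never-drinkers, and its size is unknown. Under the assumed stiffness rates it runs from nothing, through modest attenuation, to apparent protection for weak effects only under the more extreme assumptions. If former drinkers have less disease than never-drinkers, the bias goes away from the null. Loss of the factor at the univariate screen is a plausible further consequence where there is attenuation. This is a cheap improvement worth making, and it does not threaten the primary result.

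**What to change.** On the form, state the period to which the weekly average refers. Replace *None* with two answers: none, never drank regularly; and none now, but drank in the past. Ask those who tick the second for their usual past drinks per week, in the same bands.

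In the SAP, add a sentence that names alcohol as a candidate factor, makes never-drinkers the reference and keeps former drinkers as their own category.

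The cost is about one extra answer line with its follow-on band, and one SAP sentence. The downsides are a slightly longer form, imperfect recall of past intake, and a smaller reference group, with the power consequence shown above.

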FibroScan is available and has been shown to detect advancing levels of fibrosis, and it is clear that nonalcoholic fatty liver disease is increasing in prevalence throughout the western and developing worlds. Advancing liver disease leads to fibrosis, cirrhosis, and early death in a substantial portion of the population who could be helped with earlier lifestyle and medical interventions.

Vibrationcontrolled transient elastography (VCTE) is a point-of-service non-invasive technology that measures tissue elasticity and steatosis and can identify individuals at risk for disease progression and may therefore serve as an effective screening tool to alter the natural history of this disease and improve outcomes.

Changing a foundational strategy, such as responding to symptoms of liver disease, which is the current recommendation, to one of proactively intervening by screening for asymptomatic disease carries a large cost burden and is difficult to accomplish.

Objectives

The goal of this screening study is to gather FibroScan data from the at-risk but undiagnosed population on a self-selection basis so that perceived incidence rates can be calculated and the economics of a single function screening service can be evaluated.

The objective is to develop evidence based information to determine if noninvasive screening of at risk, comorbid people is feasible with this modality.

Furthermore, a secondary objective is to educate all participants about liver disease, lifestyle, healthy diets, and the role of clinical trials as part of the Foundation's larger mission of being patient advocates.

The value and necessity of clinical trials for the development of effective therapies is not well understood by the public. A goal of the foundation is to provide information about the clinical trial process to screening participants. The information is of a general nature (examples are attached). No specific trials will be mentioned. The participants will also be offered the opportunity to receive additional general education about trials and provided with links to systems in which they can explore available trials should they wish to do so. That information is of a general nature and no specific trials will be promoted. Participation in the screening will not automatically enroll them in further education as that decision is post testing and opt-in.

Questions Posed by this Study:

- What population demographics justify routine screening on a cost benefit basis?

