 - The discussion provided useful information about FDA-approved clinical trials of therapies.
 - The discussion of my liver health will help me obtain better health care for my liver.
- b. If you answered dissatisfied or very dissatisfied, please check all the reasons for your answer:
- I do not understand what the CAP-FibroScan measures.
 - I do not understand how much fat I have within my liver.
 - I am not sure if I have or do not have scarring (fibrosis) of my liver.
 - The results did not give me a better understanding of my liver health.
 - The discussion did provide useful information about FDA-approved clinical trials of therapies.
 - The discussion of my liver health is unlikely to help me obtain better health care for my liver.

SUNN STUDY

STATISTICAL ANALYSIS PLAN

PRIMARY OUTCOME MEASURE – DETERMINE THE INCIDENCE AND STAGING OF UNDIAGNOSED NAFLD AND NASH IN A HEALTH CONSCIOUS SELF SELECTED POPULATION AS MEASURED WITH A FIBROSCAN

The study will measure the incidence and severity of the fat content and liver stiffness in an at large, self selected population who do not, at the time of testing, have a diagnosis of NAFLD, NASH or other liver disease. This will measure the incidence of undiagnosed liver disease and the statistical distribution of the disease staging in this population.

A key secondary outcome measure will be the incidence and disease distribution as a function of ethnicity.

We will analyze data using a standard statistical software package, Stata® 12.1 (Stata Corp, College Station, TX). We will express continuous variables using the mean \pm standard deviation, and we will test the null-hypothesis using the Student t-test. We will compare categorical variables using contingency table analysis. For all statistical tests, we will define a two-sided p-value of ≤ 0.05 as statistically significant. We will perform multivariate analysis of all risk factors found to be statically significant ($p \leq 0.05$) using univariate analysis.

Data Analysis

We will record all data in a Microsoft Excel worksheet. We will sequentially number each participating subject. We will not record any identifying information (e.g., names, initials, DOB, SSN, insurance, EPIC MRNs) in the database. Thus, all data assessments will maintain the anonymity of all participating subjects.

1. The primary goal is to calculate the proportion of men and women that when tested have CAP-FibroScan evidence of:
 - No fat or liver stiffness

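### The primary outcome is called incidence of undiagnosed NAFLD and NASH, but one scan gives the prevalence of fat and raised stiffness; no rule identifies NASH or links alcohol to a NAFLD case

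*Combined protocol and SAP*

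**What the plan says.** The SAP's Primary Outcome Measure is to "DETERMINE THE INCIDENCE AND STAGING OF UNDIAGNOSED NAFLD AND NASH IN A HEALTH CONSCIOUS SELF SELECTED POPULATION AS MEASURED WITH A FIBROSCAN". The text beneath it describes a population of people who "do not, at the time of testing, have a diagnosis of NAFLD, NASH or other liver disease", and adds: "This will measure the incidence of undiagnosed liver disease". The key secondary outcome uses the same term: "A key secondary outcome measure will be the incidence and disease distribution as a function of ethnicity". In the protocol, the Objectives section collects FibroScan data "so that perceived incidence rates can be calculated", and Intended Use of the Data promises "data on the incidence and staging of NAFLD and NASH, as indicated by their FibroScan scores".

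The calculation itself is under Data Analysis in the SAP. The primary goal is to "calculate the proportion of men and women that when tested have CAP-FibroScan evidence of" each of six findings: neither fat nor stiffness; stiffness without fat; "Fat without liver stiffness"; fat together with stiffness; stiffness in the cirrhosis range; and stiffness in the fibrosis range short of cirrhosis. A note under the list rules out following any individual.

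Disease Staging gives a stiffness table with one row for NAFLD and NASH combined, and a CAP table that grades fat. Weekly alcohol is recorded in ten bands, from none to 21 drinks or more. Alcohol appears in neither eligibility list and in none of the six primary categories.

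**The concern.** The label implies three things that the planned figure does not contain: new onset of disease, the presence of NASH, and a non-alcoholic cause.

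This matters because Intended Use of the Data says the results should help move professional screening guidance and feed a financial model. The yield of a first screen depends on cases that already exist, and the yield of repeat screens on new ones. A model that reads a prevalence as an incidence therefore takes the wrong input. A guideline reader who takes the headline at face value would credit all detected fat and raised stiffness, whatever its undiagnosed cause, to NAFLD and NASH. If the part compatible with non-alcoholic disease is wanted later, no alcohol limit has been set, so a single figure for it would rest on a choice made after the data are seen.

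**Working it through.** The only sample-size figures in the plan are a minimum of 400 participants for power of about 0.8, and a maximum of 1,000. No expected rate or effect size is given, so the power figure cannot be reproduced. This point does not depend on it. The check is mostly a comparison of texts.

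**1. Incidence or prevalence.** The word is used six times for the study's own results: once in Objectives, once in Intended Use of the Data, and four times in the SAP's Primary Outcome Measure section (the heading, the sentence on fat content and stiffness, the sentence on undiagnosed liver disease, and the ethnicity outcome). The use in the Overview is background and is not counted. Incidence needs people known to be free of the condition at the start, and time in which new cases can arise. Participants here lack a diagnosis, which does not show that they lack disease, and each is scanned once. A proportion at testing is a prevalence. The aggregate tracking mentioned in Intended Use of the Data concerns responses to educational material, not new disease.

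**2. NASH.** The classification rules are the stiffness table and the CAP table. The first stages fibrosis in one combined row and the second grades fat. Neither separates NASH from fat alone, and none of the six categories names it. Step 1 of the study procedures has staff tell participants that the scan is not a diagnosis.

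**3. Alcohol.** With no limit in eligibility or in the primary categories, a participant with fat in the top band enters the same category as one who drinks nothing.

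**4. Bands.** In both copies of the form, 9-10 overlaps 10-12 and 13-14 overlaps 14-20. A cut of the form *at most k drinks a week* works only if no band contains both k and k+1.

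- As printed: k = 0, 2, 4, 6, 8, 12, 20, so seven usable cuts.
- With 11-12 and 15-20 in place of 10-12 and 14-20: k = 10 and 14 are added, so nine.

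**5. Size, as an illustration only.** Every input here is assumed. Let s be the share of participants above the limit (5% to 15%), with fat in 40% of those below it and in a proportion q of those above it (30% to 80%). The all-participant proportion is (1 - s) × 0.40 + s × q.

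| q | s = 5% | s = 15% | Difference from 40% |
|---|---|---|---|
| 30% | 39.5% | 38.5% | -0.5 to -1.5 points |
| 40% | 40.0% | 40.0% | 0 |
| 60% | 41.0% | 43.0% | +1.0 to +3.0 points |
| 80% | 42.0% | 46.0% | +2.0 to +6.0 points |

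For scale, the 95% half-width of the all-participant figure, 1.96 × √(p(1-p)/n) with p from 38.5% to 46.0%, is 4.8 to 4.9 points at n=400 and 3.0 to 3.1 at n=1,000. That is the precision of the overall proportion. It is not the uncertainty of the difference between that proportion and a subgroup nested within it.

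**6. Precision of a below-limit figure.** With p = 40% and 5% to 15% of participants above the limit (both assumed):

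- n=400: 4.8 points for everyone; 4.9 with 380 below the limit and 5.2 with 340.
- n=1,000: 3.0 points for everyone; 3.1 with 950 below the limit and 3.3 with 850.

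**The case against.** The strongest reply is that this is mainly a label, and that the text qualifies it. The heading says the measure is by FibroScan, the sentence beneath it names fat content and stiffness, Intended Use of the Data refers to scan scores, Objectives calls the rates perceived, and the calculation is plainly a proportion at testing. Renaming changes no computed number. This stands as a limit on weight. It does not remove the point, because these qualifiers say how the measurement is made and none of them turns a prevalence into an incidence.

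On NASH, the plan always pairs it with NAFLD and never promises a separate NASH figure. That is right. What remains is that the outcome names a condition that no planned category can show.

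On alcohol, a reader might infer that the answers go unused. The documents do not support that. The alcohol form sits in the SAP's own Data Collection section, and the secondary goal looks for factors associated with fat, using contingency tables. Fat by alcohol band could be tabulated with no limit chosen. But that table is not prespecified, and an association does not define a NAFLD case.

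A reader might also infer that people with other liver diseases contaminate the result, because the form asks about them. Staff confirm before consent that no liver disease has been diagnosed, and the documents do not show that this check fails, so no such claim is made here.

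**Conclusion.** The point holds as a mismatch between the named outcome and the planned quantity, and it is worth correcting before enrolment. The plan estimates the prevalence of FibroScan-detected fat and raised stiffness in self-selected people with no diagnosed liver disease. It does not estimate incidence, does not identify NASH, and does not separate non-alcoholic fat from other fat. The band overlap is minor: it matters only for a limit at 10 or 14 drinks, and the documents use neither.

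Two stronger readings should be resisted. One is that the primary analysis is invalid; the six proportions can be computed and are sound descriptions. The other is that drinkers inflate the reported figure. The documents give no rate of fat and no distribution of drinking, so neither the size nor the direction of any effect can be derived. Under the assumed inputs above the difference runs from -1.5 to +6.0 points and is zero if fat is equally common on both sides of the limit. Taking drinkers out of the numerator while leaving them in the denominator would always lower the figure, but that is a different quantity and is not evidence of bias.

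**What to change.** 1. In Objectives, in Intended Use of the Data, and in the SAP's primary and key secondary outcomes, replace both the word incidence and the references to staging of NAFLD and NASH with: prevalence of FibroScan-detected fat and raised stiffness, and its distribution by stage, in people with no diagnosed liver disease. Keep the six categories. State that NASH and the cause of fat or stiffness are not established.
2. Alongside the all-participant figures, report the fat categories by alcohol band, and one presumed-NAFLD proportion: fat with or without stiffness, among analysed participants below a weekly alcohol limit. The sponsor chooses the limit, at a band edge, before seeing the data. Participants with no alcohol answer stay in the all-participant figure only, and their number is reported. The ethnicity outcome uses the all-participant categories.
3. In both copies of the alcohol form, change 10-12 to 11-12 and 14-20 to 15-20 before enrolment.

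The cost is wording, two corrected bands, one descriptive table and one further proportion on a slightly smaller denominator, with the loss of precision worked out above (at most about 0.4 points at n=400 under those assumptions). No test or visit is added. Undiagnosed liver disease of other causes cannot be removed, so the added figure must stay labelled as presumed.
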